7.1.2. Planned Efficacy Statistical Analyses

Primary Statistical Analyses
Endpoint(s)

 • Percentage of subjects making at least one critical error after reading the PIL(s)
Model Specification

 • The primary endpoint of the percentage of subjects making at least one critical error after reading the PIL(s) will be analysed using the Intent-to-treat population. • This endpoint will be analysed using conditional logistic regression with subject as fixed strata, and treatment option and period as fixed effects. • Country will be included in the model providing there are sufficient subjects distributed to enable the model to run. If the model will not run with country in the model then country will be removed from the model.
Model Checking & Diagnostics

 • Refer to Appendix 9: Model Checking and Diagnostics for Statistical Analyses.
Model Results Presentation

 • The odds ratio, 95% CI and p-value will be presented for the comparison between treatment options. It will be based on a two-sided hypothesis testing approach of superiority.
SAS Code

 • Logistic regression will be used to calculate the odds ratio with 95% CI and p-value. The following SAS code will be used: <pre> proc logistic data=errors; class device period country; strata subject; model error = country device period / expb; oddsratio device; run; </pre> 
error is derived as shown in Section 11.5.3

Sensitivity and Supportive Statistical Analyses

- A sensitivity analysis will be performed using the Cochran-Mantel-Haenszel (CMH) test. The CMH test serves as a stratified approximation to the Mainland-Gart test, a variation of a one-sample chi-square test that accounts for study inhaler sequence (period). A subject who had an error with both devices or who had no errors with both devices does not provide any information about the superiority of either device. Only those subjects who had error(s) in one device and had no error in the other device are counted for in the Mainland-Gart test.
- SAS code for the CMH test is provided below:

```
proc freq data=errors (where=(err_ord^=0));
    tables seq*err_ord/cmh;
run;
```

As with the main analysis, country will be included as a covariate if sufficient data is available as described above. err_ord is derived as shown in Section [11.5.3](#)

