11.4.2. Reporting Process & Standards

Reporting Process	
Software	

 The currently supported versions of SAS software will be used. The currently supported versions of TSCG software will be used. 	
Reporting Area	
HARP Server	: uk1salx00175
HARP Area	/arenv/arprod/gsk2834425/mid206215/final_01
QC Spreadsheet	/arenv/arwork/gsk2834425/mid206215/final_01/documents
Analysis Datasets	

 Analysis datasets will be created according to Legacy GSK A&R dataset standards. 	
Generation of RTF Files	

 RTF files will be generated for use in writing the CSR. 	

Reporting Standards	
General	

 • The current GSK Integrated Data Standards Library (IDSL) will be applied for reporting, unless otherwise stated: 
 ○ 4.03 to 4.23: General Principles ○ 5.01 to 5.08: Principles Related to Data Listings ○ 6.01 to 6.11: Principles Related to Summary Tables ○ 7.01 to 7.13: Principles Related to Graphics 	
Formats	

 • All data will be reported according to the actual treatment option the subject received unless otherwise stated. • GSK IDSL Statistical Principles (5.03 & 6.06.3) for decimal places (DP's) will be adopted for reporting of data based on the raw data collected. • Numeric data on listings will be reported at the precision collected on the eCRF. 	
Planned and Actual Time	

 • Reporting for Data Listings: 
 • Unscheduled or unplanned readings will be presented within the subject's listings but not presented in summary tables. 	
Descriptive Summary Statistics	
Continuous Data	Refer to IDSL Statistical Principle 6.06.1
Categorical Data	N, n, frequency, %
Graphical Displays	

 • Refer to IDSL Statistical Principals 7.01 to 7.13. 	

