11.5.3. Critical and Overall Errors

Critical and Overall errors

An ordinal variable (error) will be derived to indicate where a participant had any error, or any critical error whilst demonstrating correct device use. If the subject has an overall/critical error the error=Y whilst if they did not have an overall/critical error then error=N. The variables errty/errtycd will be used to determine whether the variable error is referring to a critical or overall error.

An ordinal variable (err_ord) will be derived to indicate the responses of critical error based on comparing responses for the device sequences used. This variable will be used in the sensitivity analysis for critical error data.

If the sequence of inhaler use is ELLIPTA in the 1st period and DISKUS + HandiHaler or Turbuhaler + HandiHaler in the 2nd period, then for critical error in relation to sequence:
 
 err_ord = -1, if subject had critical error in the 1st period but NOT in the 2nd period err_ord = 1, if subject had critical error in the 2nd period but NOT in the 1st period err_ord = 0, if subject had critical errors in BOTH periods or had NO critical errors in BOTH periods

If the sequence of inhaler use is and DISKUS + HandiHaler or Turbuhaler + HandiHaler in the 1st period and ELLIPTA in the 2nd period, then for each preference question:
 
 err_ord = 1, if subject had critical error in the 1st period but NOT in the 2nd period err_ord = -1, if subject had critical error in the 2nd period but NOT in the 1st period err_ord = 0, if subject had critical errors in BOTH periods or had NO critical errors in BOTH periods

The above method also applies to overall errors.

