Number of Subjects who failed to demonstrate correct use (censored)	XXX	XXX
Median Time to demonstrate correct inhaler use (minutes) [1]	XXX	XXX

[1] The Median Time to demonstrate correct inhaler use (minutes) is taken from the Kaplan-Meier analysis. If more than 50% of the data is censored then the median is not applicable.
Note: For the Diskus+Handihaler and Turbuhaler +HandiHaler groups, if a subject made an error on one device and not the other the time to demonstrate correct use is censored at the total of time taken for both devices.

Programming notes: Page by sub-study and assessment (Time taken to read the PIL and Demonstrate Correct Use/ Time for HCP Instruction and to Demonstrate Correct Use /Total Time to demonstrate correct use).

Example : EFF_T03
Protocol : 206215
Population : Intent to Treat

Table X.X
Summary and Analysis of Treatment Preference

Sub-study 1: ELLIPTA vs DISKUS + HandiHaler

	Total (N=XXX)	P-Value

Which treatment do you prefer based on the number of the number of steps needed to take your medication?		
n	XXX	X.XXX
ELLIPTA	XXX (XX%)	
DISKUS + HandiHaler	XXX (XX%)	
No Preference	XXX (XX%)	
Which treatment do you prefer for taking your medication?		
n	XXX	X.XXX
ELLIPTA	XXX (XX%)	
DISKUS + HandiHaler	XXX (XX%)	
No Preference	XXX (XX%)	

Note: The p-value is from the Cochran-Mantel-Haenszel Test.
Programming notes: Page by sub-study. %'s calculated out of the small n for each question.

Example : EFF_T04
Protocol : 206215
Population : Intent to Treat

Table X.X
Analysis of Percentage of Subjects making at least one Critical Error

Sub-study 1: ELLIPTA vs DISKUS + HandiHaler
Assessment: After reading the PIL(s)

	ELLIPTA (N=XXX)	DISKUS + HandiHaler (N=XXX)
At least one Critical Error	XXX (XX%)	XXX (XX%)
Zero Critical Errors	XXX (XX%)	XXX (XX%)
ELLIPTA vs DISKUS + HandiHaler		
Odds Ratio	X.XX	
95% CI	(X.XX, X.XX)	
p-value	X.XXX	

Note: Odds ratio, 95% CI and p-value obtained from a conditional logistic regression model. Subject is included in the model as fixed strata, treatment option, country and period included as fixed effects.

Programming notes: Page by sub-study and assessment

Example : EFF_T05
Protocol : 206215
Population : Intent to Treat

Table X.X
Summary and Analysis of Number of Instructions from the HCP

Sub-study 1: ELLIPTA vs DISKUS + HandiHaler

	ELLIPTA (N=XXX)	DISKUS + HandiHaler (N=XXX)	Difference (ELLIPTA – DISKUS+HandiHaler)
n	X	X	X
Median (95% CI)	XXX (XXX – XXX)	XXX (XXX – XXX)	XXX (XXX – XXX)

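### The primary-analysis code sets neither the event level nor the device reference, so under SAS defaults the odds ratio and its interval come out inverted in at least one sub-study; the p-value is unaffected

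*SAP*

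**What the plan says.** SAP 7.1.2 gives the SAS code for the primary endpoint. The classification statement is "class device period country", the model statement is "model error = country device period / expb", and the odds ratio is requested with "oddsratio device". None of these carries an event level, a sort-order option, a reference level or a parameterisation option. The response is defined in SAP 11.5.3: "If the subject has an overall/critical error the error=Y whilst if they did not have an overall/critical error then error=N".

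The results text in 7.1.2 gives no direction: "The odds ratio, 95% CI and p-value will be presented for the comparison between treatment options". The direction appears only in mock shell EFF_T04 (SAP 11.12). Its title is "Analysis of Percentage of Subjects making at least one Critical Error" and its comparison row is labelled "ELLIPTA vs DISKUS + HandiHaler". The target is therefore the odds of at least one critical error, ELLIPTA against the comparator.

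SAP 11.4.1 lists the treatments both by letter code (A, B, C) and by display name. It does not say which of these the variable device holds. On software, SAP 11.4.2 says only this: "The currently supported versions of SAS software will be used". No default is overridden anywhere.

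**The concern.** Two things decide which way an odds ratio points: which response level counts as the event, and which treatment is the reference. The code leaves both to sort order, and sort order does not deliver the contrast in the shell. The headline estimate and its 95% CI could then be the reciprocal of what the table title says, in one sub-study or in both. If only one is inverted, two consecutive pages of the same table would show the same effect on opposite sides of 1.

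The p-value gives no warning, because it is the same in every case. The sensitivity shell EFF_T07 reports counts and a p-value but no odds ratio, so there is no second odds ratio to compare with. Sections 8.1.2.1, 8.1.2.2 and 9.1.1.1 refer back to the same method for the other error endpoints and inherit the defect wherever the model is fitted.

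**Working it through.** The plan states no expected odds ratio, so there is none to reproduce. Its related figure, at least 90% power (protocol 10.2), does not depend on this point, because a two-sided test is the same whichever level is the event or the reference.

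**Inputs**
- Response Y or N: SAP 11.5.3.
- Code without event or reference: SAP 7.1.2.
- Possible values of device: SAP 11.4.1.
- Planning rates, first row 11% v 37% and last row 6% v 29%: protocol 10.2. The comparator rates are the stated minima.
- SAS defaults (general knowledge of the software, not document text): a binary response models the first ordered level; classification variables use effect coding; the ODDSRATIO statement compares the first sorted level with the later one.

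**Step 1: event.** N sorts before Y, so the code models the odds of no error.

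**Step 2: size of the target.** For paired binary data with no period effect, the conditional odds ratio is the probability of an error on ELLIPTA only, divided by that of an error on the comparator only. Assuming independence within subject:
- 11% v 37%: (0.11 × 0.63) / (0.37 × 0.89) = 0.0693 / 0.3293 = 0.21; reciprocal 4.75.
- 6% v 29%: (0.06 × 0.71) / (0.29 × 0.94) = 0.0426 / 0.2726 = 0.16; reciprocal 6.40.

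**Step 3: combine event and device order.** The target is 0.21 in every row.

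| device holds | Sub-study | Sort order | Odds ratio the code returns | At 11% v 37% |
|---|---|---|---|---|
| Codes | 1 | A (ELLIPTA), B | No error, ELLIPTA v comparator | 4.75 |
| Codes | 2 | A (ELLIPTA), C | No error, ELLIPTA v comparator | 4.75 |
| Names | 1 | DISKUS + HandiHaler, ELLIPTA | No error, comparator v ELLIPTA | 0.21 |
| Names | 2 | ELLIPTA, Turbuhaler + HandiHaler | No error, ELLIPTA v comparator | 4.75 |

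In the third row both the event and the contrast are reversed, so the value equals the target.

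**Step 4: numerical check.** A constructed data set has 72 pairs, 36 per sequence:
- ELLIPTA first: 3 with an error on ELLIPTA only, 12 on the comparator only, 1 on both, 20 on neither.
- Comparator first: 2, 12, 2 and 20 in the same order.

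The error rates are 8/72 = 11.1% and 27/72 = 37.5%. With treatment and period in the conditional model, the odds ratio for an error, ELLIPTA v comparator, is √[(3/12) × (2/12)] = 0.204. The standard error of its logarithm is ½√(1/3 + 1/12 + 1/2 + 1/12) = 0.5, so the 95% CI is 0.077 to 0.544 and p = 0.0015. Taking no error as the event gives 4.90 (1.84 to 13.0). Fits with either event and either reference gave one of these two values, always with p = 0.0015. They were run in Python; SAS itself was not run.

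**Step 5: the exponentiated coefficient.** Under effect coding the two devices are scored +1 and −1, so the log odds ratio is twice the coefficient. The column that the expb option prints is then the square root of the odds ratio: 2.21 where the odds ratio is 4.90, or 0.45 where it is 0.204. It is not the figure the table needs.

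**The case against.** The strongest reply is that this is a flaw in a code fragment and not in the analysis. EFF_T04 already fixes the contrast and prints, directly above the odds ratio, the number and percentage of subjects with a critical error on each treatment. An odds ratio of 4.75 beneath 11% and 37% would look wrong on the same page. EFF_T06 and EFF_T07 give the discordant counts by device, Figure 2.01 shows the percentages again, and the reporting area in SAP 11.4.2 includes a QC spreadsheet. The inverted estimate is an exact reciprocal and can be recovered. All of this stands: the target is defined, and the error may well be caught. It does not make the code right, because SAP 7.1.2 says this is the code that will be used, and as written it does not produce the table it feeds.

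A reader might infer that the code returns 4.75 in both sub-studies, or that the two sub-studies must point in opposite directions. The documents support neither as a certainty. These are alternatives that depend on what device holds, which the SAP leaves open: with codes both are inverted and agree with each other, and with names only sub-study 2 is inverted.

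**Conclusion.** The defect is real and limited to the estimate. Under SAS default ordering the prespecified code models the odds of no error. Under either labelling in SAP 11.4.1, at least one sub-study reports the reciprocal of the intended odds ratio and CI. The size is 4.75 in place of 0.21 at 11% v 37%, and 6.40 in place of 0.16 at 6% v 29%, both assuming independence within subject and no period effect. Which sub-studies are affected depends on the unstated content of device.

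A reader might also infer that the primary conclusion is at risk. It is not: the hypotheses in SAP 2.4 are two-sided, and the test, p-value, significance decision and power are the same in every case. Nor is the target of estimation missing, since EFF_T04 shows it. The conclusion rests on the SAS defaults listed above and on nothing outside the SAP overriding them.

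**What to change.** In SAP 7.1.2:
- Name the event in the model statement: `error(event='Y')`.
- Name the comparator of each sub-study as the reference in the classification statement: `device(ref='<comparator>')`.
- Request the contrast as `oddsratio device / diff=ref`.
- Report the odds ratio and CI from the ODDSRATIO output and not from the expb column.
- Add one sentence: the odds ratio compares the odds of at least one critical error on ELLIPTA with those on the comparator, and a value below 1 favours ELLIPTA. Adapt the wording for the overall-error endpoints.

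The event and the reference should be changed together. Naming the event alone, with display names in device, would give 4.75 in sub-study 1 and 0.21 in sub-study 2.

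The country term should stay as SAP 7.1.2 and the EFF_T04 footnote have it. Whether it belongs in a model stratified by subject is a separate matter, and dropping it here would create a new mismatch between text and code.

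The cost is small edits to three statements and one sentence of text, with no effect on design, data, power or the test.

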7.2. Method of Treatment Assignment

All participants will be centrally randomized using an Interactive Web Response System (IWRS). Before the study is initiated, the log in information & directions for the IWRS will be provided to each site.

Participants will be assigned in equal numbers to one of four sequences for the sub-study they are included on, in accordance with the randomization schedule generated by Clinical Statistics, prior to the start of the study and using validated internal software.

The possible sequences for each sub study are shown in Table 1 and Table 2

Table 1 Sub Study 1 Treatment Sequences

Sequence	Period 1	Period 2	Preference Questionnaire
A	ELLIPTA	DISKUS + HandiHaler	1
B	DISKUS + HandiHaler	ELLIPTA	2
C	ELLIPTA	DISKUS + HandiHaler	2
D	DISKUS + HandiHaler	ELLIPTA	1

Table 2 Sub Study 2 Treatment Sequence

Sequence	Period 1	Period 2	Preference Questionnaire
E	ELLIPTA	Turbuhaler + HandiHaler	3
F	Turbuhaler + HandiHaler	ELLIPTA	4
G	ELLIPTA	Turbuhaler + HandiHaler	4
H	Turbuhaler + HandiHaler	ELLIPTA	3

Study treatments will be dispensed at the study visit summarized in SOA

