10.2. Sample Size Determination

The sample size calculation for each sub-study is based on the primary endpoint, the percentage of subjects making at least one critical error in each device combination (Ellipta or DISKUS - HandiHaler or Turbuhaler - HandiHaler) after reading the patient information leaflet(s).

Based on the results from studies 201301 and 201330, a range of critical error rates (at least one critical error using each device after reading the patient information leaflet) for each of the treatment options (ELLIPTA, DISKUS - HandiHaler and Turbuhaler - HandiHaler) were explored.

Using 10000 simulations, a total of 72 subjects in each sub-study will provide at least 90% power to show a statistically significant difference between the critical error rate of each of the paired treatment options (Sub-study 1: Treatment option 1 vs. Treatment Option 2; Sub-study 2: Treatment option 1 vs. Treatment Option 3) assuming the following true critical error rates.

Treatment Option 1:	Treatment Option 2:	Treatment Option 3:
ELLIPTA Critical Error Rate	DISKUS - HandiHaler Critical Error rate	Turbuhaler - HandiHaler Critical Error rate
11%	>=37%	>=37%
10%	>=35%	>=35%
9%	>=34%	>=34%
8%	>=32%	>=32%
7%	>=31%	>=31%
6%	>=29%	>=29%

The error rates for the combined treatment options were based on the studies 201301 and 201330 and a conservative assumption that the critical error rate for the combined treatment was the same as the critical error rate for a single device i.e. subjects who made errors made them on both devices.

Conditional logistic regression and a two-sided 5% significance level were used as the analysis method in the simulations. No withdrawal is expected in this single visit study however up to 80 subjects may be randomised to each sub-study to ensure we have 72 evaluable subjects in each sub-study.

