8.1.2.2. Number of overall errors made

Secondary Statistical Analyses
Endpoint(s)

 • Percentage of subjects making at least one overall error after reading the PIL(s) • Percentage of subjects making at least one overall error after the first instruction from the HCP
Model Specification, Model Checking & Diagnostics, Model Results Presentation

 • Same method as percentage of subjects making at least one critical error after reading the PIL(s), see Section 7.1.2 • Sensitivity analysis will also be performed as detailed in Section 7.1.2 • Note this model will only be fitted if there is sufficient data. If there is insufficient data then only summary statistics will be produced.

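### The sensitivity CMH code in SAP 7.1.2 reads the primary model's multi-row data set with no reduction to one record per subject; if `err_ord` sits on both period rows, its false-positive rate is about 17–19% instead of about 5%

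*SAP*

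**What the plan says.** The primary model in SAP 7.1.2 is "proc logistic data=errors; class device period country; strata subject; model error = country device period / expb". Device and period vary within a subject, and subject is the stratum.

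The sensitivity test in the same section begins "proc freq data=errors (where=(err_ord^=0" and requests the CMH statistics for `seq*err_ord`. The printed code has no period filter, weight or de-duplication step. The text above it makes the subject the counting unit: only subjects with an error on one treatment option and none on the other contribute.

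On the variable itself, SAP 11.5.3 states: "An ordinal variable (err_ord) will be derived to indicate the responses of critical error based on comparing responses for the device sequences used". This gives one value per subject. The section does not say whether the value is stored on one row or on both.

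For overall errors, SAP 8.1.2.2 adds: "Sensitivity analysis will also be performed as detailed in Section 7.1.2". The results go to shell EFF_T07, which reports the number of discordant subjects and a CMH p-value.

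**The concern.** A data set that serves the primary model holds at least two rows per subject. A subject-level value kept there as an ordinary variable repeats on each row, and the filter on `err_ord` keeps or drops both rows together. PROC FREQ treats rows as independent observations, so it would see twice as many discordant subjects as exist.

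This is the only sensitivity analysis that 7.1.2 specifies for the primary endpoint. With duplicated rows, its p-value in EFF_T07 would be too small, and so would the one for overall errors. The number-of-instructions and preference analyses name data sets of their own (`no_error`, `pref_data`). That suggests a separate subject-level file was simply not named here, although the SAP does not state the row structure of those files either.

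**Working it through.** **Inputs.**
- Significance level, Protocol 10.2: "Conditional logistic regression and a two-sided 5% significance level were used as the analysis method in the simulations". The SAP sets no separate level for the sensitivity test, so two-sided 5% is used.
- Size, Protocol 10.2: "a total of 72 subjects in each sub-study will provide at least 90% power", for ELLIPTA against comparator error rates of 11/37, 10/35, 9/34, 8/32, 7/31 and 6/29%.
- Allocation, Protocol 7.2: "Participants will be assigned in equal numbers to one of four sequences". Two of the four sequences have each inhaler order, so 72/2 = 36 subjects per order.
- Assumption, not in the documents: errors on the two options are independent within a subject (correlation varied from 0 to 0.2 for the power check).

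**1. The plan's own figure.** Simulated power at the six rate pairs under independence:

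| Test | Power |
|---|---|
| Likelihood ratio, with period | 96–97% |
| McNemar | 96–98% |
| Exact McNemar | 94–95% |
| Wald, without period | 92–96% |
| Wald with period, estimable runs only | 93–95% |

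The stated floor of 90% is met. The Wald test with period falls below it (57–82%) only if runs with an empty cell count as non-significant. At correlation 0.2, the likelihood-ratio and McNemar tests reach about 99%, and Wald without period gives 77–93%. The inputs are therefore read as the plan intends.

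**2. Effect of duplication.** For one 2×2 table with D discordant subjects, Q = (D − 1)φ². Copying every row leaves φ unchanged and gives Q = (2D − 1)φ². The ratio (2D − 1)/(D − 1) is slightly above 2.

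Illustration (hypothetical counts): 22 discordant subjects, 4/8 in one order and 7/3 in the other.
- φ² = (4·3 − 8·7)²/(12·10·11·11) = 1936/14520 = 0.133
- Counted once: Q = 21 × 0.1333 = 2.80, p = 0.094
- Counted twice: Q = 43 × 0.1333 = 5.73, p = 0.017

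**3. Size.** For large D, doubling is like testing the correct statistic against 3.84/2 = 1.92: 2[1 − Φ(1.96/√2)] = 16.6%.

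Simulation with no device and no period difference, 36 + 36 subjects, 100,000 runs per rate. The mean number of discordant subjects is 2 × 72 × p(1 − p).

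| Error rate on both options | Mean discordant | Once, period-coded / as in 11.5.3 | Twice, period-coded / as in 11.5.3 |
|---|---|---|---|
| 6% | 8.1 | 3.9 / 4.1% | 18.8 / 19.0% |
| 11% | 14.1 | 4.9 / 4.8% | 18.3 / 18.0% |
| 20% | 23.0 | 5.0 / 5.0% | 17.6 / 17.7% |
| 29% | 29.6 | 4.8 / 5.0% | 17.0 / 17.3% |
| 37% | 33.6 | 5.0 / 4.9% | 17.2 / 17.1% |
| 50% | 36.0 | 4.9 / 4.9% | 17.1 / 17.1% |

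With D fixed at single values from 10 to 72, discreteness widens the range: 4.1–6.0% counted once, 13.9–19.9% counted twice.

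**4. What the table tests.** In 11.5.3, −1 means an error on ELLIPTA only, in both orders. Crossing that with sequence asks whether the device contrast differs by order, which is a period effect. In 11.5.4, `pref_ord` = −1 means the first-period treatment is preferred in both orders, which is the layout a device comparison needs. Rejection rates with each subject counted once:

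| Setting | As coded in 11.5.3 | Coded by period |
|---|---|---|
| 11 vs 37%, no period effect | 4.2% | 96.1% |
| 6 vs 29%, no period effect | 3.0% | 96.4% |
| 30% on both, period odds ratio 1.5 | 18.8% | 4.8% |
| 30% on both, period odds ratio 2 | 44.4% | 4.9% |
| 30% on both, period odds ratio 3 | 80.4% | 4.7% |

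**The case against.** The code is schematic. Neither block filters on sub-study, assessment or error type, although 11.5.3 says other variables separate critical from overall errors. Reading the sensitivity code literally on row structure alone is therefore selective. The text above it and EFF_T07 both make the subject the unit, and EFF_T06 reports the discordant count, so a doubled total would not match it. A programmer who follows the text and shells could well build one record per subject. If `err_ord` were filled on one row and missing on the other, PROC FREQ would drop the missing row by default and nothing would be inflated.

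Much of this stands. A reader might infer that every discordant subject will certainly be counted twice; the documents do not support that, because they do not say where `err_ord` is stored. A reader might also infer that a non-significant primary result could be declared confirmed. No section gives the sensitivity p-value a decision role. At the planned differences, a correctly coded test counted once already rejects about 96% of the time, so doubling would seldom change its conclusion.

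The objection does not remove the gap. The text and shells state the intended unit, nothing in the printed code enforces it, and the missing filters could only add rows.

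**Conclusion.** The point holds conditionally. If `err_ord` is carried on both rows, the sensitivity CMH test has a size of about 17–19% instead of about 5%. The figures assume two rows per subject, 72 subjects split 36:36, independence within subject, no country stratum, and no period effect. Under period-based coding, doubling still gives about 17% when a period effect is present (17.2–17.5% for period odds ratios of 1.5 to 3).

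The reach is limited to the sensitivity test for critical errors and, by 8.1.2.2, overall errors. The conditional logistic regression needs its two rows per subject and is not affected.

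A reader might also infer that removing duplicates makes the p-value right. It does not. With `err_ord` coded as in 11.5.3, the de-duplicated test rejects in only 3–4% of runs at the two ends of the planned range (11/37% and 6/29%), and it reacts to a period effect instead. De-duplication is necessary but not sufficient.

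**What to change.** 1. In SAP 7.1.2, run the sensitivity test on a named data set (for example `errors_subj`) with one record per subject for the given sub-study, error type and assessment. Apply this to overall errors through 8.1.2.2 as well.
2. Add a programming check that the total in the CMH table equals the number of discordant subjects in EFF_T06 and EFF_T07, allowing for any records lost to a missing stratification variable.
3. In SAP 11.5.3, code `err_ord` by period in both orders, in the manner of `pref_ord` in 11.5.4, so that `seq*err_ord` compares devices.

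The cost is one line for the input data set, one check, and a corrected derivation for one sequence order. No data collection, sample size or primary analysis changes. Step 1 alone makes the sensitivity p-values larger where rows would have been duplicated. Only steps 1 and 3 together make them valid for the device comparison.
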